## 1 PURPOSE

This statistical analysis plan (SAP) describes the statistical methods to be used during the reporting and analysis of data collected under the Bovie Medical Corporation study, “A Prospective, Multicenter, Single Arm Clinical Study Evaluating the Use of J-Plasma® for Dermal Resurfacing.”

## 2 SCOPE

This SAP should be read in conjunction with the study protocol and electronic case report forms (eCRFs). This version of the plan has been developed with respect to Study protocol version 1, dated 31 July 2017. Any further changes to the protocol or eCRF may necessitate updates to the SAP.

## 3 APPLICABLE DOCUMENTS

Document Number	Document Title
VP-1558	A Prospective, Multicenter, Single Arm Clinical Study Evaluating the Use of J-Plasma® for Dermal Resurfacing Study Protocol
STATSOP-002	Statistics Standard Operating Procedure – Statistical Analysis Plan
SRS vX	Study Requirements Specification (includes Case Report Form requirements)

## 4 SOFTWARE

All tables, listings and figures will be primarily produced using SAS Version 9.3 (SAS Institute, Cary, NC) or a later version of SAS.

## 5 ABBREVIATIONS AND DEFINITIONS

Abbreviation	Definition
AE	Adverse Event
CRF	Case Report Form
DRM	Data Review Meeting
eCRF	Electronic Case Report Form
FAS	Full Analysis Set
FSS	Fitzpatrick Skin Scale
FWS	Fitzpatrick Wrinkle and Elastosis Scale
Modified GAIS	Modified Global Aesthetic Improvement Scale
ITT	Intent to Treat
PPS	Per Protocol Set
SAE	Serious Adverse Event
SAP	Statistical Analysis Plan
UADE	Unanticipated Adverse Device Effect
VAS	Visual Analog Scale

## 6 STUDY OBJECTIVES

The primary objectives of this study are to demonstrate the safety and efficacy of the J-Plasma system for use in dermal skin resurfacing.

## 7 STUDY ENDPOINTS

### 7.1 Primary Efficacy Endpoint

The primary efficacy endpoint of this clinical investigation is a comparison of the proportion of subjects (i.e. percentage of treatment responders) with a  $\geq 1$ -score improvement on the Fitzpatrick Wrinkle and Elastosis Scale (FWS) at the 3 month visit, as compared to baseline as determined by at least 2 out of 3 blinded Independent Photographic Reviewers. The study design assumes a 75% success rate of subjects with treated wrinkles with a  $\geq 1$ -score change on the FWS.

### 7.2 Primary Safety Variable

The primary safety variable is the evaluation of adverse events through 3 months post-treatment.

### 7.3 Secondary Efficacy Endpoint

Subjects with a  $\geq 1$ -score improvement on the FWS and at least a self-reported “improved” rating on the modified GAIS at the 3-month visit will be considered to have an aesthetic pleasing outcome. The modified GAIS is a measure of aesthetic improvement relative to the baseline, pre-treatment condition.

### 7.4 Secondary Safety Variable

The secondary safety variable is the evaluation of the pain and discomfort after treatment as reported by the subject on a visual analog scale (VAS).

### 7.5 Additional Endpoints

Other endpoints to be evaluated include:

1. FWS  $\geq 1$ -score improvement and  $\geq 75\%$  agreement with at least an “improved” rating by the subject on the modified GAIS. The modified GAIS is a measure of aesthetic improvement relative to the baseline, pre-treatment condition.
2. Magnitude of improvement measured by the mean change in FWS from baseline to 3 months visit.
3. Subject satisfaction with procedure recorded at the 3-month visit.
4. Achievement of re-epithelialization by facial zone and across all facial zones at the 10 day, 1-month and 3-month follow-up visits as reported by the investigator.
5. Mean duration until study subject feels comfortable going in public after treatment as reported by the study subject.
6. Daily 10-point Visual Analog Scale (VAS) pain assessment following treatment through the 10 day follow-up visit by diary day with a change from the VAS pain score at baseline.

## 8 STUDY DESIGN

### 8.1 Overview

This is a multi-center, single arm, evaluator-blind prospective study of 55 study subjects who are seeking a procedure to reduce the appearance of wrinkles and rhytides at up to 5 investigational centers in the United States.

Study subjects that meet study eligibility criteria and have provided informed consent will be enrolled in the study. During the procedure, the investigators will use J-Plasma® on applicable facial zones to reduce wrinkles and rhytides.

Study subjects will be followed immediately following the procedure, at 10 days, 1, 3, and 6 months post-procedure for study assessments.

Study enrollment is expected to occur over 3-6 months. Imaging and study assessments will continue through 6 months post-procedure. Total study duration is expected to be approximately 9-12 months. It is expected that the 510(k) application for the device will be submitted based on 3 month post-procedure results. However, this clinical trial will continue until every enrolled subject has reached 6 months following their procedure. At that time, the trial will be considered complete, the final results will be determined, and a final report will be prepared.

**Table 1. Study Required Procedures**

	Baseline/ Pre- Procedure Screening 	Procedure	10 Days	1 mo	3 mo	6 mo
			10+4/-1 days	30±7 days	90±10 days	180±14 days
Informed Consent	✓					
Assess Inclusion/Exclusion Criteria	✓					
Urine Pregnancy Test 	✓	✓				
Medical History	✓					
General Physical Exam	✓					
Review Medications	✓		✓	✓	✓	✓
Photographic Images 	✓		✓	✓	✓	✓
Fitzpatrick Skin Scale (FSS)	✓					
Fitzpatrick Wrinkle and Elastosis Scale (FWS) 	✓		✓	✓	✓	✓
Visual Analog Scale (10-point VAS) 		✓	✓	✓	✓	✓
Study Procedure		✓				
Subject Diary (10-point VAS) 		✓	✓			
Adverse Event Assessment		✓	✓	✓	✓	✓
Re-epithelialization and Down Time 			✓	✓	✓	
Modified Global Aesthetic Improvement Scale (GAIS) 			✓	✓	✓	✓

 Pre-procedure Screening assessments to take place within 21 days prior to undergoing the procedure.  
 Up to two urine pregnancy tests must be obtained prior to study procedure for females with child-bearing potential (one at pre-procedure screening and one on the day of the procedure prior to the procedure if screening and procedure are not performed on the same day).  
 Digital photographs of the subject's face will be taken and labeled according to Photography Instructions.  
 To be completed by Investigator and Independent Photographic Reviewers (IPRs).  
 To be completed by the study subject on a day of the procedure (prior to the procedure and immediately following the procedure) and at all follow-up visits.  
 To be completed by the study subject daily starting from the day of procedure (after procedure, at home) until the 10 day follow-up visit.  
 To be completed by Investigator and/or Independent Photographic Reviewer (as applicable) to capture achievement of epidermal recovery status at follow-up visits; and date when study subject felt comfortable, willing and able to go in public following study procedure (assessed at the 10 day follow-up visit).  
 To be completed by Investigator and study subject at all study follow-up visits.

## 8.2 Randomization

This is a single arm study, thus randomization is not used.

## 8.3 Blinding

The primary efficacy endpoint is the comparison of the proportion of subjects (i.e. percentage of treatment responders) with a  $\geq 1$ -score improvement on the FWS at the 3-month visit, as compared to baseline as determined by at least 2 out of 3 blinded Independent Photographic Reviewers.

#### 8.4 Sample Size Considerations

The objective of this study is to demonstrate that study participants positively respond to the J-Plasma® therapy, thus the primary endpoint will be assessed via the percentage of study participants that demonstrated an improvement in the FWS from baseline to the 3-month visit. An improvement is clinically important when there is  $\geq 1$ -score change. The planned sample size to provide sufficient power for a statistical comparison of the proportion of treatment responders (P) versus a reasonable cutoff ( $P_0$ ) was based on a power calculation utilizing the (one proportion) binomial exact test based on the following assumptions.

- $H_0: P \leq P_0$  versus  $H_a: P > P_0$
- Type I error rate:  $\alpha = 0.05$  (one-sided)
- Population proportion under the null hypothesis:  $P_0 = 0.75$
- Population proportion under the alternative hypothesis:  $P = 0.90$
- Total N: 50 study participants

Based on the above assumptions, the study power is estimated to be approximately 88%. To account for possible missing data (up to 10% attrition), a total of 55 subjects will be enrolled. Other tests (i.e., a test of the mean improvement of FWS) would be expected to provide more power.

One study investigating the effects of radiofrequency energy on the improvement of appearance of wrinkles and rhytides (De Novo, Newa™) utilized a FWS cutoff as 75%, supporting this value in the present sample size computation.

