### 9.2 Missing Data

If applicable, a list of subjects who were withdrawn/lost to follow-up from the study and associated reasons will be provided.

Subjects with missing 3-month FWS data will be imputed as having no change from baseline. No other imputations for missing data will be employed. Furthermore, no estimation of missing data for self-reported pain within the 10 day Subject Diary will be imputed.

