#### 10.2.2 Full Analysis Set (FAS)

All subjects enrolled in the study who have a FWS value at baseline will be included in the FAS. Subjects with missing FWS data at the 3-month visit will be imputed as no change and included in the FAS population. Efficacy outcomes will be evaluated in the FAS.

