### 10.5 Primary Efficacy Endpoint Analyses

The primary efficacy endpoint is the comparison of the proportion of subjects (i.e. percentage of treatment responders) with a  $\geq 1$ -score improvement on the FWS at the 3-month visit, as compared to baseline as determined by at least 2 out of 3 blinded Independent Photographic Reviewers. The study design assumes a 75% success rate of subjects with treated wrinkles with a  $\geq 1$ -score change on the FWS. The percentage

of subjects with a  $\geq 1$ -score improvement will be summarized as counts and percentages. This percentage will be compared to the cutoff of 75% using a binomial exact test (one-sided). Descriptive upper 95% confidence limit will be provided for the difference between treatment and cutoff rate and the associated p-value will also be provided.

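### The 88% power assumes dropouts leave the analysis, but the SAP counts them as non-responders among 55; at the attrition ceiling power is about 25–31%

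*SAP*

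**What the plan says.** Section 8.4 plans a one-sided exact binomial test of the responder proportion at the 0.05 level. The null rate is 0.75, the alternative is 0.90 and N is 50. From these inputs "the study power is estimated to be approximately 88" percent. The section then raises enrolment: "To account for possible missing data (up to 10% attrition), a total of 55 subjects will be enrolled".

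The missing-data rule is in section 9.2: "Subjects with missing 3-month FWS data will be imputed as having no change from baseline". Section 10.2.2 repeats it and fixes the denominator: "Subjects with missing FWS data at the 3-month visit will be imputed as no change and included in the FAS population". The FAS is every enrolled subject with a baseline FWS, and it is the population for the efficacy outcomes.

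Section 10.5, like section 7.1, describes the design differently from section 8.4: "The study design assumes a 75% success rate of subjects with treated wrinkles". It goes on to name 75% as the cutoff for the test.

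**The concern.** Enrolling 55 so that 50 remain after attrition makes sense when dropouts are excluded from the analysis. Here they are not. A responder must improve by at least one FWS point, so a subject imputed as unchanged is always a failure. The five additional subjects do not replace those lost: the denominator stays at 55 and each lost subject adds a failure. Section 8.4 does not lower the 90% rate to allow for this.

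The consequence is a false-negative trial. Section 8.1 expects the 510(k) application to rest on the 3-month results. A device that reaches the assumed rate among the subjects assessed could miss its primary endpoint through attrition alone, and the SAP has no planned analysis that would separate that miss from a device failure.

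A smaller, related problem is that sections 7.1 and 10.5 present 75% as the assumed success rate, whereas section 8.4 makes it the null value.

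**Working it through.** **Inputs.** One-sided level 0.05, null rate 0.75, alternative 0.90, N = 50, up to 10% attrition and 55 enrolled (section 8.4). Exact binomial test against 75% (section 10.5). Missing 3-month FWS counted as no change and kept in the FAS (sections 9.2 and 10.2.2).

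**Method.** For a given n, the critical value r is the smallest count with P(Bin(n, 0.75) ≥ r) ≤ 0.05.

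**Step 1: the SAP's own figure.** For n = 50, r = 43.
- P(Bin(50, 0.75) ≥ 43) = 0.0453
- P(Bin(50, 0.90) ≥ 43) = 0.8779

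This reproduces the stated 88%, which therefore describes 50 subjects with complete data.

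**Step 2: the test on the FAS of 55.** For n = 55, r = 47.
- P(Bin(55, 0.75) ≥ 46) = 0.0888, too large
- P(Bin(55, 0.75) ≥ 47) = 0.0454

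**Step 3: a fixed number d missing.** All d are failures, so the 47 responders must come from the 55 − d observed subjects. Power = P(Bin(55 − d, 0.90) ≥ 47).

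| Missing (d) | Observed | Response needed among observed | Power |
|---|---|---|---|
| 0 | 55 | 47/55 = 85.5% | 90.6% |
| 1 | 54 | 47/54 = 87.0% | 83.2% |
| 2 | 53 | 47/53 = 88.7% | 72.3% |
| 3 | 52 | 47/52 = 90.4% | 57.9% |
| 4 | 51 | 47/51 = 92.2% | 41.3% |
| 5 | 50 | 47/50 = 94.0% | 25.0% |

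From three missing onward, the response needed among observed subjects exceeds the assumed 90%. Ten percent of 55 is 5.5; with six missing, power is 12.0%.

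**Step 4: random attrition at rate a.** The FAS response rate becomes 0.90 × (1 − a), and power = P(Bin(55, 0.90 × (1 − a)) ≥ 47).

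| Attrition | FAS response rate | Power |
|---|---|---|
| 5% | 0.90 × 0.95 = 0.855 | 59.7% |
| 5/55 = 9.1% | 0.90 × 50/55 = 0.818 | 31.0% |
| 10% | 0.90 × 0.90 = 0.81 | 25.8% |

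**Step 5: what would restore the stated power.** With five missing, solving P(Bin(50, p) ≥ 47) = 0.88 gives p of about 0.96. The response rate among observed subjects would have to be about 96%, not 90%.

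**Step 6: the 75% wording.** If 75% were the true rate, as sections 7.1 and 10.5 suggest the design assumes, the test on 55 subjects would succeed with probability 0.0454. That is simply its type I error.

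**The case against.** The strongest reply is that 10% is a ceiling. With nobody missing power is 90.6%, and with one missing it is 83.2%; both are acceptable. That is true, and 25–31% should be read as power at the top of the allowance. But the allowance exists to protect power up to that ceiling, and power is already 72.3% with two missing (2/55 = 3.6%).

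Second, section 8.4 does not say whether 0.90 applies to assessed subjects or to the FAS after imputation. If it is the FAS rate, power at 55 is 90.6% whatever the attrition. The assumption has to be declared. On that reading, however, dropouts are already in the 90% and the step from 50 to 55 has no purpose, so the assessed-subject reading is the natural one.

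Third, counting missing as failure is conservative and does not inflate the type I error. That stands; the imputation rule is not the defect. The defect is a power statement that ignores it.

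Fourth, the Per Protocol Set might seem to supply the missing comparison. It does not: section 10.2.3 defines it by major deviations rather than by missing data, and efficacy is repeated on it only if its size differs from the ITT population by at least 10%.

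Fifth, section 10.5 names 75% as the cutoff, so the loose wording is unlikely to mislead whoever runs the test. That is fair: the wording is a minor point, though it does conflict with section 8.4.

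Finally, restating the power does not raise it. That is also true: the remedy makes the risk visible and the result interpretable, and power will then depend on retention to the 3-month visit.

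**Conclusion.** The concern holds. The 88% is correct for 50 subjects with complete data, but the SAP does not plan that analysis. Under its own missing-data rule, power at the attrition ceiling is 25.0% with exactly five missing, and 25.8% to 31.0% under random attrition of 10% and 5/55. It falls below 80% once two subjects are missing and below 50% once four are missing.

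These figures assume that all 55 enrolled subjects have a baseline FWS and so enter the FAS, and that 90% is the response rate among subjects assessed at 3 months. The description of 75% as the assumed success rate in sections 7.1 and 10.5 is a separate, minor error.

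**What to change.** 1. Rewrite section 8.4 for the analysis to be run, for example: FAS of 55; reject the null with 47 or more responders (exact level 0.0454); at 90% response among assessed subjects, power is 91% with none missing, 72% with two and 25% with five, because a missing 3-month FWS counts as non-response.
2. Delete the statement that 55 subjects offset 10% attrition.
3. In sections 7.1 and 10.5, state that 75% is the null performance goal and that the design assumes 90%.
4. Keep missing-as-non-response as the primary analysis, and add one sensitivity analysis restricted to subjects with an observed 3-month FWS, so that a miss caused by attrition can be told from a miss caused by the device.

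The cost is SAP wording and one extra table. The stated power becomes less favourable. No extra subjects are needed, and the primary test, population and imputation rule do not change.

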## 9 DATA STRUCTURE AND HANDLING

### 9.1 Data Handling and Transfer

Data management will be undertaken by NAMSA Data Management. NAMSA Biostatistics will either be provided access to download SAS datasets or NAMSA Data Management will provide them upon request.

Programming of analysis datasets, tables, figures and listings will be conducted during the data management phase of the study. Tables, figures, and listings may be reviewed prior to final data lock for data review. Any data values requiring investigation or correction will be identified, and protocol deviations will be reviewed. The final run of outputs will take place after the data is deemed final.

### 9.2 Missing Data

If applicable, a list of subjects who were withdrawn/lost to follow-up from the study and associated reasons will be provided.

Subjects with missing 3-month FWS data will be imputed as having no change from baseline. No other imputations for missing data will be employed. Furthermore, no estimation of missing data for self-reported pain within the 10 day Subject Diary will be imputed.

### 9.3 Visit Windows

All data attributed to a time point per the CRF will be included in the analysis of that time point, regardless of if it is out of window. Unscheduled visit data will be included in summaries that are not specific to a time point.

### 9.4 Pooling Data Across Sites

Pooling of outcome data from different clinical study sites will be performed by evaluating the homogeneity of the efficacy endpoint across sites, using the Chi-square test statistic. If homogeneity is demonstrated across sites, then the endpoint results will be combined across all clinical study sites.

If significant heterogeneity is observed amongst sites (significant difference in Chi-square test), then the primary endpoint will be additionally presented with a random site adjusted estimate and confidence interval.

Sites with less than five (5) patients enrolled will be combined into a pseudo-site for purposes of analysis. To protect against having an overly large pseudo-site, when one pseudo-site exceeds ten subjects, a second pseudo-site will be formed. This process will continue as needed each time a pseudo-site exceeds ten subjects.

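### SAP section 9.4 reads a non-significant site test as proof of homogeneity and shows the site-adjusted estimate only after a significant one, although the test has low power for moderate site differences

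*SAP*

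**What the plan says.** Section 9.4 (Pooling Data Across Sites) compares the efficacy outcome between centers, "using the Chi-square test statistic. If homogeneity is demonstrated across sites, then the endpoint results will be combined across all clinical study sites". When the test is significant, "then the primary endpoint will be additionally presented with a random site adjusted estimate and confidence interval". The section gives neither a significance level for this test nor an alternative for sparse tables. Sites with fewer than five subjects are merged into pseudo-sites.

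The setting comes from other sections. Section 8.1 allows up to five centers. Section 8.4 bases power on "Total N: 50 study participants" and enrols 55 to cover attrition. It assumes a null response rate of 0.75 and states "Population proportion under the alternative hypothesis: $P = 0.90" for the alternative. Section 9.2 counts a missing 3-month FWS as no change. The subgroup list in section 10.11 (age, gender, race/ethnicity, FSS) does not include site, so section 9.4 is the only place where the SAP provides for site-level information on the primary endpoint.

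**The concern.** Three features of section 9.4 combine badly.

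- **The inference.** Failing to reject equality across sites is not evidence of equality. It could be informative only if the test had good power against differences that matter, and section 9.4 gives no power for it.
- **The gate.** The site-adjusted estimate appears only when the test rejects. If real differences are often missed, the supplementary result is often absent when it is relevant.
- **The open level.** Section 8.4 sets 0.05 one-sided for the primary test. No level is set for the site test, so the trigger could be settled after the data are seen.

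This matters because the trial is single-arm and the treatment is delivered by an operator. With no control group within a site, differences between sites go straight into the responder rate. Section 8.1 expects a 510(k) submission on the 3-month results, where consistency across sites is a natural question.

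**Working it through.** **1. The SAP's own figure.** Section 8.4: exact binomial, N = 50, null 0.75, alternative 0.90, one-sided 0.05. The critical value is 43 responders:

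- P(X ≥ 43 | 50, 0.75) = 0.0453
- P(X ≥ 43 | 50, 0.90) = 0.878

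This reproduces the stated 88%. The SAP gives no corresponding figure for the site test.

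**2. Expected non-responders per site** = site size × (1 − response rate). An equal split is an assumption.

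| Layout | Response rate | Expected per site |
|---|---|---|
| 5 sites, N = 50 | 0.90 | 10 × 0.10 = 1.0 |
| 5 sites, N = 55 | 0.90 | 11 × 0.10 = 1.1 |
| 5 sites, N = 55, 10% missing counted as non-responders | 0.90 × 0.90 = 0.81 | 11 × 0.19 = 2.09 |
| 5 sites, N = 55 | 0.75 | 11 × 0.25 = 2.75 |
| 3 sites of 18 to 19 | 0.90 | 1.8 to 1.9 |

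All are below the usual minimum of 5. The pseudo-site rule does not help, because it merges only sites with fewer than five subjects.

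**3. Power of the site test.** The Pearson statistic is Σ (xᵢ − nᵢp̄)² / [nᵢ p̄(1 − p̄)], where xᵢ of nᵢ subjects respond at site i and p̄ is the pooled rate. It is referred to chi-square with (sites − 1) degrees of freedom. Simulation used 200,000 trials per scenario, so the Monte Carlo standard error is at most √(0.25/200,000) = 0.0011. N = 55 and the level is an assumed 0.05.

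| Sites | True site rates | Power | Not detected |
|---|---|---|---|
| 5 × 11 | 70%, four at 90% | 21% | 79% |
| 5 × 11 | 70%, four at 95% | 38% | 62% |
| 5 × 11 | 100, 95, 90, 85, 80% | 16% | 84% |
| 5 × 11 | 60%, four at 95% | 63% | 37% |
| 5 × 11 | 50%, four at 90% | 64% | 36% |
| 4 (14, 14, 14, 13) | 70% (a site of 14), three at 95% | 51% | 49% |
| 3 (18, 18, 19) | 70% (a site of 18), two at 95% | 57% | 43% |
| 2 (27, 28) | 70% (the site of 27), 95% | 74% | 26% |
| 3 (18, 18, 19) | 70% (a site of 18), two at 90% | 33% | 67% |

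With random (beta) site rates averaging 90% at five sites of 11, power is 8%, 25% and 44% for between-site standard deviations of 5, 10 and 15 points.

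**4. Effect of the unstated level.** For five sites, one at 70% and four at 95%, the adjusted estimate would appear in 38% of trials at 0.05, 52% at 0.10 and 54% at 0.15.

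**5. Size of the test when sites are truly equal** (five sites of 11, nominal 0.05): 0.031 at a 90% rate and 0.045 at 81%. The approximation is mildly conservative at the SAP's own rate.

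**The case against.** The strongest reply is that nothing decisive depends on this test. Section 10.5 fixes the primary analysis as a one-sided exact binomial test against 75%, with no condition on site homogeneity. Section 9.4 says that the adjusted estimate is presented additionally, so the pooled result is reported either way. This stands, and it limits the point to the reading of site consistency and to one supplementary estimate.

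Stronger readings are tempting, but the SAP does not support them:

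- **That the rule would usually hide a clearly worse site.** This holds for moderate differences at about five sites. It fails for a very poor site (63% power at 60% against 95%) and for several layouts with fewer sites. Section 8.1 says up to five centers, so five is the sparsest case.
- **That the chi-square approximation is invalid.** At the 90% rate the size is 0.031, a minor fault. An inflated size of 0.085 can be produced, but it needs a 95% rate and sites of 5, 5, 5, 20 and 20, neither of which is in the SAP. The same layout at 90% gives 0.059.
- **That the report must declare homogeneity shown.** Section 9.4 uses that idea as a condition for combining sites. It prescribes no such statement in the report.

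Two further objections also stand. An exact test would not cure low power. And with at most five sites and few non-responders, a random-site variance is poorly estimated, so the site rates themselves are the more informative output.

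**Conclusion.** The point holds in limited form and should be corrected. Section 9.4 draws an inference that its test cannot support, and makes a supplementary result conditional on that test at an unstated level. With five sites of 11, a 0.05 level and rates near the SAP's 90%, moderate site differences would go undetected in about 62% to 84% of trials. The equal split, the 0.05 level and the site-rate patterns are assumptions. Fewer sites, a more liberal level or a more extreme outlier raise the power. The logical fault, taking non-significance as evidence of homogeneity, does not depend on any of them. The primary test, its error rate and the pooled estimate are untouched.

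**What to change.** In section 9.4:

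- Remove demonstrated homogeneity as a condition for pooling, and state that the pooled result is primary in all cases.
- Always report the responder rate for each site or pseudo-site with an exact 95% confidence interval.
- Always report the random-site-adjusted estimate as a supportive analysis, whatever the test shows.
- If a homogeneity test is kept, label it descriptive, state its level, and say that a non-significant result is not evidence of homogeneity.

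The cost is a change of wording and one extra table. Sample size and the primary hypothesis do not change. The drawback is that the random-site variance will be imprecise with at most five sites, and the report should say so beside the estimate.
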